## **B) Study Objectives:**

### **7. Aim of the study:**

This study is conducted to evaluate the clinical performance of low-shrinkage giomer resin composite versus resin-modified glass ionomer in restoration of cervical caries lesions, using both Modified USPHS and Revised FDI criteria.

### **Hypothesis:**

This study will be designed to test the null hypothesis that the low-shrinkage giomer resin composite will have the same clinical performance as resin-modified glass ionomer in cervical restorations, using both Modified USPHS and Revised FDI criteria.

### **Primary Objectives:**

Measure the functional, biological, and aesthetic properties of both restorations (using Revised FDI criteria for direct restorations) at baseline, after 6, and 12 months.

### **Secondary Objectives:**

Measure Cost-Effectiveness Analysis: Cost-effectiveness will be assessed by calculating the Incremental Cost-Effectiveness Ratio (ICER) and the Cost per Success Ratio (CPSR).

## **C) Trial Design**

- Study design: Randomized clinical trial (parallel group, two arm study).
- Triple-blinded (participants, outcome assessors and statisticians).
- Allocation ratio; 1:1
- Framework: Superiority frame.

## **PICOTS Elements:**

**P (Population):** Adult patients with cervical carious lesions in maxillary anterior teeth (ICDAS II score 4).

**I (Intervention):** Low Shrinkage, giomer paste-like resin composite (Beautifil™ II LS, Shofu Inc, Kyoto, Japan).

**C (Comparison):** Light cured resin reinforced glass ionomer restorative Fuji II LC® (GC Corporation, Tokyo, Japan).

### **Outcomes:**

#### **a) Primary Objectives:**

Measure the functional, biological, and aesthetic properties of both restorations (using Revised FDI criteria for direct restorations) at baseline, after 6, and 2 months.

#### **b) Secondary Objectives:**

Measure Cost-Effectiveness Analysis: Cost-effectiveness will be assessed by calculating the Incremental Cost-Effectiveness Ratio (ICER) and the Cost per Success Ratio (CPSR).

**T (Time):** 12 months; with follow up at baseline, 6, and 12 months.

**S (Study design):** Randomized clinical trial.

### **III. Methods**

#### **A) Participants, interventions, and outcomes**

##### **9. Study setting:**

This clinical trial will be held in the Conservative Dentistry Department, Faculty of Dentistry, Cairo University, Egypt.

##### **10. Eligibility Criteria of study population:**

###### Inclusion Criteria of participants:

- Moderate to high caries-risk patients with carious cervical lesions (ICDAS score 4) in maxillary anterior teeth.
- Patients with at least 20 teeth under occlusion.
- Age: 25-50 years.
- Asymptomatic vital teeth.
- Co-operative patients approving to participate in the trial.

###### Exclusion Criteria of participants:

- Patients younger than 25 years old or older than 50 years old.
- Extensive cervical lesions extending beyond proximal line angles.
- Teeth with signs and symptoms of irreversible pulpitis or pulp necrosis.
- Teeth supporting removable prostheses, or orthodontic appliances.
- Candidates with parafunction or bruxism.
- Candidates with systemic diseases or disabilities that may affect participation.
- Drug-induced xerostomia.
- Known allergy to resin-based composites or RMGIs.
- Heavy smoking.
- Pregnancy.
- Lack of compliance.

##### **11. Proposed Intervention:**

###### **Clinical examination:**

- For every patient, medical and dental history, caries risk assessment profile, and salivary flow test will be obtained. If bleeding on probing of the gingiva is positive, scaling will be performed at least 1 week before restoration.
- Clinical examination will be done by mouth mirror, explorer, dentin hypersensitivity test using compressed air through triple syringe, and standardized photographs.

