### **Review of literature:**

The development of cervical lesions in permanent dentition may be related to carious or non-carious origin. Class V caries lesions may occur due to different factors

such as poor oral hygiene, dietary habits, or xerostomia (*Akarsu et al, 2021*).

Management of cervical lesions presents serious problems with any restorative material. The two most common reasons for restoration failure are secondary caries at the tooth-restoration interface and loss of retention (*AlQranei et al, 2021*). Class V lesions often exhibit a low retentive cavity configuration (C-factor); which is responsible for marginal gaps around the restorations (*AL-Gailani et al, 2019*). Cervical margins -lying in either dentin or cementum- show unfavorable bonding performance (*Kim et al, 2017*), besides being usually subgingival where moisture control is difficult (*Zhang et al, 2021*). The subgingival margin is not clinically desirable due to difficulty in cleaning and increased biofilm accumulation (*AlQranei et al, 2021*). Therefore, the selection of the restorative material can be challenging.

In this context, fluoride containing adhesive materials are considered ideal in restoring class V carious lesions. Resin modified glass ionomers (RMGI) are highly recommended in the restoration of cervical lesions. The most important advantages of glass ionomer are its chemical adhesion to the tooth structure, and its fluoride release (*Toz-Akalin et al, 2023*). However, RMGI has lower weakness and esthetic properties compared to resin composite (*AlQranei et al, 2021*).

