### 14. Sample size calculation:

The sample size was calculated based on a previous study by *Vural et al in 2021*, in which percentage of successful class V restorations (Score A and B) using resin modified glass ionomer regarding marginal discoloration was 68.7%. By implementing a two tailed Z test for difference between two independent proportions with an alpha level of 5% and a power of 80%. The minimum sample size needed was 23 per group in order to detect a difference of 30%. Sample size was increased by 20% to compensate for possible dropouts to reach 28 teeth per group. Sample size was performed using G\*Power version 3.1.9.2 for windows.

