### 15. Patient Recruitment:

Patients will be recruited by [name] using stratified sampling method until reaching to the target sample size. They will be recruited from clinic of conservative dentistry department in Faculty of Dentistry, Cairo University, where there is a continuous and high patient flow from which eligible patients will be recruited to fulfill the eligibility criteria 1 month before intervention.

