## **B) Assignment of interventions:**

### **16. Allocation:**

#### **16. a) Random sequence generation (Randomization):**

[name] will perform simple randomization according to a check list, including the number of participants by generating numbers from 1 to 56, divided into two groups denoted with letter A and B. Randomization will be generated using ([www.randomization.com](http://www.randomization.com)).

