### **20. Statistical analysis plan:**

#### **a) Statistical Methods:**

Data will be analyzed using Medcalc software, version 19 for windows (MedCalc Software Ltd, Ostend, Belgium). Categorical data will be described as frequency and percentage. Intergroup comparisons between categorical variables will be performed using the chi square test, while intragroup comparisons within each intervention will be performed using Cochran's Q test followed by pairwise multiple comparisons. A p-value less than or equal to 0.05 will be considered statistically significant and all tests will be two tailed. The statistical power of the study will be set at 80 % with 95 % confidence level.

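### Caries risk is measured on every patient before allocation but, once eligibility is settled, is used neither to balance the arms nor in comparing them, so a chance imbalance would go uncorrected

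*Combined protocol and SAP*

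**What the plan says.** All places are in the combined protocol and SAP.

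- **Measurement.** Section 11, Clinical examination: "For every patient, medical and dental history, caries risk assessment profile, and salivary flow test will be obtained". The participant timeline (section 13) puts baseline data collection one month before the intervention and randomization at the intervention visit.
- **Eligibility.** Section 10 admits "Moderate to high caries-risk patients with carious cervical lesions (ICDAS score 4) in maxillary anterior teeth". Low-risk patients are therefore kept out, while two risk levels enter. Drug-induced xerostomia is excluded, but no salivary-flow cut-off is given.
- **Rationale.** The literature review lists causes of class V caries, "such as poor oral hygiene, dietary habits, or xerostomia". The statement of the problem gives secondary caries as one of the two commonest reasons for restoration failure. The rationale argues the need for a suitable material with reference to high caries-risk patients and expects giomer to reduce secondary caries.
- **Recruitment.** Section 15 recruits "using stratified sampling method until reaching to the target sample size" and names no strata.
- **Allocation.** Section 16a: the responsible person "will perform simple randomization according to a check list", using numbers 1 to 56 split into groups A and B. No strata or blocks are mentioned.
- **Analysis.** Section 20a: "Intergroup comparisons between categorical variables will be performed using the chi square test". No stratified, adjusted or sensitivity analysis is planned, and no baseline comparison by arm is mentioned.

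**The concern.** Biological properties are one of the three domains of the primary outcome, and by the protocol's own reasoning they depend on the patient's caries risk as well as on the material. In a small trial one arm can draw noticeably more high-risk patients by chance. That arm's restorations would then look somewhat worse (or the other arm's better) for a reason unrelated to the material, and the planned comparison makes no allowance for it. The information needed to prevent or correct this is in hand before the envelope is opened. What is at stake is the credibility and interpretation of one realized estimate, not the validity of randomization.

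**Working it through.** **Inputs from the documents.** Section 14: control success 68.7%, difference 30 points, two-sided alpha 5%, power 80%, 23 per group raised to 28.

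**Assumed, because the documents give nothing.** One tooth per patient; high-risk share p = 50% (30% or 70% as alternatives); success lower by e = 10, 20 or 30 points in high-risk patients.

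**1. The plan's own figure.** Reading the difference as 68.7% v 98.7%, the mean is 0.837 and

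n = [1.960·√(2·0.837·0.163) + 0.842·√(0.687·0.313 + 0.987·0.013)]² / 0.30² = 22.6, so 23 per group.

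23 × 1.2 = 27.6, so 28. The stated size reproduces.

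**2. How often the arms differ in caries risk.** With two independent Binomial(28, p) counts of high-risk patients:

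| Difference between arms | p = 50% | p = 30% or 70% |
|---|---|---|
| at least 4/28 (14 points) | 35.0% | 30.7% |
| at least 6/28 (21 points) | 14.1% | 10.8% |

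The model matters a little. If exactly 28 of the 56 patients are high-risk and the arms are 28/28 (hypergeometric), the two figures are 42.3% and 18.1%. If allocation is a coin toss and the arm sizes vary, they are 30.0% and 11.6%.

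**3. What an imbalance does to the estimate.** Shift = e × imbalance.

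- 14 points: 0.143 × 10, 20, 30 = 1.4, 2.9, 4.3 points.
- 20 points: 2, 4, 6 points.
- 25 points: 2.5, 5, 7.5 points.

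**4. What it does to the test.** Simulation with 28 per arm, half the patients high-risk, 200,000 runs per scenario; unadjusted chi-square against a Cochran-Mantel-Haenszel test stratified by risk, success as yes/no.

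| | Unadjusted | Stratified |
|---|---|---|
| Type I error, all randomizations | 5.3% | 4.9% |
| Type I error given imbalance of 20 points or more, e = 10 | 5.8% | 5.1% |
| same, e = 20 | 6.5% | 4.9% |
| same, e = 30 | 8.6% | 5.1% |
| Power at the planned 30-point effect | 95.3–95.4% | 94.2–95.1% |

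These powers exceed the 88.1% that the formula in step 1 gives at n = 28, because the normal approximation is poor near 100% success. Only the contrast between columns is used here. With stratified allocation and the stratified test, power is 95.4–96.0%.

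**5. What restores balance.** Separate envelope lists without blocks do not: with coin-toss allocation, imbalances of 14 points or more occurred in 30.2% of simulated trials with two lists and 30.0% with one. Permuted blocks of 4 within each risk level reduced them to essentially none.

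**The case against.** The strongest reply is that chance imbalance is already covered by the test's error rate, so an unadjusted randomized comparison needs no repair. This stands as far as it goes. A reader might infer that the planned chi-square test is biased or has inflated error; averaged over randomizations it does not, and 8.6% arises only given a large imbalance and an assumed 30-point prognostic effect. What remains is that the trial yields one estimate, which a visible imbalance would leave open to doubt.

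Four other inferences go further than the documents allow.

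- *The documents show that these markers predict outcome.* They do not. The literature review names causes of the lesion, which every participant already has. No section says that caries risk or salivary flow predicts 12-month FDI scores, and the trial is sized on marginal discoloration. The link through secondary caries makes caries risk a plausible prognostic factor, with an unknown effect.
- *The measurements are never used.* Caries risk serves eligibility. The gap begins after screening.
- *Precision is being thrown away.* At the planned effect the stratified test gains no power. Any gain elsewhere is small and depends on the assumed effect.
- *Section 15 shows that stratified randomization was intended.* It speaks of sampling and names no strata. It needs clarifying, but shows no such intention.

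**Conclusion.** The concern holds in a limited form. A plausible prognostic factor, known before allocation, plays no part in allocation or in the arm comparison. Under a 30% to 50% high-risk share, a difference of 14 points or more between arms would arise in roughly 30% to 42% of trials, depending on the model (35% in the base case). A larger imbalance of 20 to 25 points would move the estimate by about 2 to 7.5 points if high risk costs 10 to 30 points of success. That is small against the 30-point design difference, but it would matter for a borderline result. The textual gap is certain. The sizes rest entirely on the assumed share and effect. This is an inexpensive improvement to the design and does not invalidate the planned test.

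**What to change.** - **Section 16a:** replace simple randomization with permuted-block randomization, with concealed block sizes, stratified by caries risk (moderate or high).
- **Section 15:** say what the stratified sampling refers to, or remove the term.
- **Section 20a:** make the arm comparison stratified by caries risk (Cochran-Mantel-Haenszel), or prespecify that comparison as a sensitivity analysis. Report caries risk and salivary flow by arm.
- **If recruitment has begun:** leave allocation alone and apply only the stratified analysis.

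A regression on salivary flow is not advised. At 98.7% success, the chance of no failure at all among 28 giomer restorations is 0.987^28 = 0.69, so an ordinary logistic model would often fail to converge to usable estimates.

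The cost is two blocked envelope lists instead of one and a line in the analysis plan; no new data are needed. The limitation is that only one two-level factor can be carried at this sample size.

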## **Restorative procedures:**

### **- Cavity preparation procedures for both the intervention and control groups:**

After giving local anesthesia, the operative field will be isolated using rubberdam by performing multiple teeth isolation with at least two teeth before and after tooth to be treated. Using a water-cooled high-speed handpiece (380.000-480.000 rpm), class V cavity will be prepared on the facial surface of the tooth using a pear-shaped diamond bur (MANI Ltd., Utsunomiya, Japan), and then a bevel is prepared 45° on the incisal wall of the cavity using a diamond finishing tapered bur (MANI Ltd., Utsunomiya, Japan). The bur will not be used for more than 3 cavity preparations. Any remaining soft carious dentin will be excavated by a small, sharp excavator (Dentsply® Maillefer, Switzerland).

### **Intervention:**

Low Shrinkage, giomer paste-like resin composite (Beautifil™ II LS, Shofu Inc, Kyoto, Japan).

All materials will be applied according to the manufacturer's instructions. The prepared tooth surfaces will be rinsed and dried by gently blowing with an air syringe. Selective enamel etching will be done; where the enamel margins will only be etched with 35-40% phosphoric acid gel for 10-15 seconds, rinsed for 5 seconds and gently dried. The unfilled universal adhesive (Shofu Inc, Kyoto, Japan) will be applied onto the entire cavity surface and left undisturbed for 10 seconds. Then the adhesive will be air dried with gentle air for 3 seconds and then, dried with stronger air to dry the surface. It will be light-cured using LED light-curing unit (Light output: 1200 mW/cm^2) for 20 seconds. Beautifil™ II LS will be applied according to manufacturer's instructions as follows: shade selection will be done before rubberdam isolation. The material will be applied into the cavity using a gold-plated instrument, where incremental filling and light-curing of the material in layers, does not exceed 2 mm each. Each increment will be light-cured using LED light-curing unit (Light output: 1200 mW/cm^2) for 20 seconds. The restorations will be finished using water-cooled microfine diamond finishing burs for contouring and removal of excess restorative material and will be polished with aluminum oxide polisher immediately after filling.

### **Comparator:**

Light-cured glass ionomer restorative, available in premeasured unit dose capsules (Fuji II LC®, GC Corporation, Tokyo, Japan).

All materials will be applied according to the manufacturer's instructions. The prepared tooth surfaces will be rinsed and dried by gently blowing with an air syringe. Cavity conditioner (GC Corporation, Tokyo, Japan) will be applied for 10 seconds, rinsed, and gently dried without dessication. GC Fuji II LC™ will be dispensed according to manufacturer's instructions, followed by LED light curing (Light output: 1200 mW/cm^2) for 20 seconds. The restorations will be finished using water-cooled

microfine diamond finishing burs for contouring and removal of excess restorative material and will be polished. Then, G-COAT PLUS™ (GC Corporation, Tokyo, Japan) will be applied to finished restorations following manufacturer's instructions.

## 12. Outcomes

Outcomes will be assessed by mouth mirror, dental explorer, standardized photographs and FDI probe according to modified USPHS criteria and Revised FDI criteria for direct and indirect restorations:

- **Primary outcomes:** All restorations will be assessed for functional, biological, and aesthetic properties using Revised FDI criteria for direct and indirect restorations. They will be given a score (clinically excellent/very good, clinically good, clinically satisfactory, clinically unsatisfactory, clinically poor).
- **Secondary outcomes:** Cost-Effectiveness Analysis

Cost-effectiveness will be assessed by calculating the Incremental Cost-Effectiveness Ratio (ICER) and the Cost per Success Ratio (CPSR). These metrics will be used to compare the cost and clinical outcomes of LS-GRC and RMGI in treating class V cavities.

### *Incremental Cost-Effectiveness Ratio (ICER)*

The ICER will be used to compare the cost-effectiveness of LS-GRC versus RMGI by evaluating the additional cost for each successful outcome provided by LS-GRC compared to RMGI. The ICER will be calculated using the following formula:

$$ICER = \frac{(C_2 - C_1)}{(E_2 - E_1)}$$

Where:

- $C_2$  and  $C_1$  are the total costs of LS-GRC and RMGI, respectively,
- $E_2$  and  $E_1$  are the respective effective outcomes (i.e., clinically excellent rates after 12 months).

The cost calculation methodology will account for several key factors, including the material cost per restoration, clinical application costs, and replacement or repair costs over time. Additionally, indirect costs, such as patient time, transportation, and the number of follow-up visits, will also be considered.

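### The ICER and CPSR are planned as bare point estimates, with no measure of uncertainty and no rule for a zero or negative difference in effect

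*Combined protocol and SAP*

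**What the plan says.** Section 12 (Outcomes) names cost-effectiveness as the secondary outcome, measured by the ICER and the CPSR; the table in section 20(b) repeats this. The ICER is (C2 − C1)/(E2 − E1), where 2 is the giomer (LS-GRC), 1 is the resin-modified glass ionomer (RMGI), C is total cost and E is the clinically excellent rate at 12 months. Its stated purpose is "evaluating the additional cost for each successful outcome provided by LS-GRC compared to RMGI". The CPSR is total cost over number of successes, one ratio per material.

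Section 20(a) deals with categorical outcomes only: "Categorical data will be described as frequency and percentage", followed by chi-square and Cochran's Q tests. Neither section 12 nor section 20 gives a method for cost data, an interval for either ratio, or an instruction for a zero or negative E2 − E1. Section 20(c) adds that missing outcomes will not be imputed.

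Section 14 sizes the trial on a different endpoint. Success "using resin modified glass ionomer regarding marginal discoloration was 68.7" per cent, and "The minimum sample size needed was 23 per group in order to detect a difference of 30" percentage points.

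**The concern.** E2 − E1 is the difference between two proportions, each from at most 28 restorations. Three things follow if the formula is applied as written.

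- If the two observed rates are equal, the ICER does not exist.
- If E2 is below E1, the ratio is a number but is not an additional cost per success. It is negative if the giomer is also costlier (dominated) and positive if it is cheaper and less effective. A negative ratio also arises when the giomer is cheaper and more effective (dominant), so the sign alone cannot separate the best case from the worst.
- If E2 exceeds E1 by only a few restorations, the ratio is defined but very unstable.

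The research question asks whether the materials perform similarly, and the null hypothesis is equality. The planned summary should therefore be interpretable when the difference is small, which is where it behaves worst. At stake is the trial's only secondary conclusion: without an interval, a reader cannot tell a firm cost-effectiveness result from chance.

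**Working it through.** **The plan's own figure.** Section 14 uses a "two tailed Z test for difference between two independent proportions" "with an alpha level of 5% and a power of 80" per cent, with p1 = 0.687 and p2 = 0.687 + 0.30 = 0.987. The pooled mean is 0.837, and

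n = [1.960 × √(2 × 0.837 × 0.163) + 0.842 × √(0.687 × 0.313 + 0.987 × 0.013)]² / 0.30²
= [1.960 × 0.5224 + 0.842 × 0.4773]² / 0.09 = 22.6, so 23 per group.

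The stated 23 is reproduced. Then 23 × 1.2 = 27.6, which gives the stated 28: "Sample size was increased by 20% to compensate for possible dropouts to reach 28 teeth per group". Arms are equal ("Allocation ratio; 1:1").

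**Assumptions.** No clinically excellent rate is given for either material, so 68.7% serves only as an anchor for RMGI. It is a marginal-discoloration success rate, not the ICER's effect measure. Restorations are treated as independent. No costs are given.

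**Chance of a zero or negative denominator.** Let X1 ~ Bin(n, p1) and X2 ~ Bin(n, p2) be the numbers rated clinically excellent. The exact probabilities sum P(X1 = i) × P(X2 = j) over j = i (tie, ICER undefined) and over j < i (negative denominator).

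| True rates, RMGI / LS-GRC | Tie, n = 28 | Negative, n = 28 | Together, n = 28 | Together, n = 23 |
|---|---|---|---|---|
| 68.7% / 68.7% | 11.5% | 44.3% | 55.7% | 56.3% |
| 68.7% / 78.7% | 8.4% | 15.6% | 24.0% | 27.1% |
| 68.7% / 83.7% | 5.2% | 6.7% | 11.8% | 14.9% |
| 68.7% / 88.7% | 2.3% | 1.9% | 4.2% | 6.3% |
| 68.7% / 98.7% (design) | <0.1% | <0.1% | <0.1% | 0.1% |
| 95% / 95% | 25.6% | 37.2% | 62.8% | 64.3% |

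The 23-per-arm column applies if dropout reaches the allowance, since missing outcomes are not imputed.

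**Uncertainty in the effect difference.** At 28 per arm, a 95% Newcombe interval for E2 − E1 includes zero in 94.8% of trials at no true difference, 86.6% at 10 points, 56.5% at 20 points and 8.8% at 30 points.

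**Spread of the ICER when it can be read as intended.** Assume a fixed cost difference of 100 units. If the giomer has k more excellent restorations out of 28, the ICER is 100/(k/28) = 2,800/k. Among trials with k > 0:

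| True difference (from 68.7%) | True ICER | k over the central 95% | ICER range |
|---|---|---|---|
| 20 points | 100/0.20 = 500 | 11 down to 1 | 255 to 2,800 |
| 30 points (design) | 100/0.30 = 333 | 13 down to 4 | 215 to 700 |

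These ranges reflect sampling of the effect only. Section 12 also counts repair and replacement costs, which vary between patients and are not modelled here.

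**The case against.** A reader might infer that the whole cost-effectiveness conclusion hangs on one ICER. The documents do not support that: the CPSR is planned alongside it and exists whenever an arm has at least one success, so a zero or negative E2 − E1 does not break it. But the CPSR also has no interval, and as one average ratio per arm it does not measure the cost of an extra success.

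A reader might also infer that the ICER fails in a large share of results whatever the truth. It does not. At the difference the trial is sized for, the sign problem almost vanishes, and at 20 points it is about 4%. The large shares belong to true differences of about 10 points or less. Those cannot be dismissed, because equality is the stated null and the design difference concerns another endpoint.

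Nor are all these cases undefined; only exact ties are. With a negative denominator, the analyst holds all four components and can see which material is costlier and which is more effective. Nothing says that the ratio will be published without its components, so a misleading report is a risk and not a certainty. The formula itself is standard. What stands is that the plan fixes one reading of the ratio and gives no rule for results where that reading is wrong.

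The 100-unit cost difference is an illustration. It shows relative spread and says nothing about actual costs.

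**Conclusion.** The point holds as a gap in the analysis and reporting rules for the secondary outcome; the primary outcome is unaffected. Both ratios lack any measure of uncertainty, and the ICER's stated interpretation fails whenever E2 is at or below E1. On the 68.7% anchor with 28 per arm, that is about 56% of trials under equality, 24% at 10 points, 12% at 15, 4% at 20 and under 0.1% at 30. Exact ties account for about 8 to 12% of trials at true differences of 0 to 10 points, and about 26% if both rates are 95%. The missing interval matters across the whole range: even at the design difference the illustrative ICER spans more than a threefold range. The probabilities depend on assumed clinically excellent rates. The sign of the cost difference cannot be judged from the documents.

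**What to change.** Add a paragraph to section 20:

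- Make the incremental cost and the incremental clinically excellent rate the reported results, each with a 95% interval. Bootstrap participants within arm if costs are recorded per participant. Otherwise, give an interval for the effect difference and vary the costs over a stated range.
- Say in words when one material is both cheaper and more effective.
- Quote an ICER as cost per extra success only when LS-GRC is both costlier and more effective, and show the two differences and their intervals beside it.
- Give an interval for each arm's CPSR.

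A cost-effectiveness plane or a net-benefit summary is optional. Net benefit would need a willingness-to-pay range, which the documents do not give.

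The change needs no extra participants or visits. It does need a cost record per participant for the bootstrap: section 12 lists cost components, but section 18 (Data Collection methods) mentions no cost data. The analysis is a short script. The price is a headline that becomes an interval, probably a wide one, in place of a single figure.
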